7.2 Participant Discontinuation/Withdrawal from the Study

Participants are free to withdraw from participation in the study at any time upon request.

An investigator may discontinue or withdraw a participant from the study for the following reasons:

- Pregnancy
- Significant study intervention non-compliance
- Development of new conditions that would change inclusion/exclusion criteria
- If the participant meets an exclusion criterion (either newly developed or not previously recognized) that precludes further study participation
- Participant unable to receive CT for 30 days.

The reason for participant discontinuation or withdrawal from the study will be recorded on the Case Report Form (CRF).

7.3 Lost to follow up

A participant will be considered lost to follow-up if he or she fails to return for one or more of the two study visits and is unable to be contacted by the study staff.

The following actions must be taken if a participant fails to return to the clinic for a required study visit:

- The site will attempt to contact the participant and reschedule the missed visit to the earliest available date, and counsel the participant on the importance of maintaining the assigned visit schedule and ascertain if the participant wishes to and/or should continue in the study.
- Before a participant is deemed lost to follow-up, the investigator or designee will make every effort to regain contact with the participant (where possible, 3 telephone calls, within a 1-week span). These contact attempts should be documented in the participant's study file.

Should the participant continue to be unreachable, he or she will be considered to have withdrawn from the study with a primary reason of lost to follow-up.

8 STUDY ASSESSMENTS AND PROCEDURES

8.1 Study scheme

Screening for eligibility

Prior to the appointment, patients will be identified by their UCLA dental provider as potentially needing a CT scan of the jaws for treatment planning. The patients will be prescreened by a member of the research team for age eligibility. The study staff will coordinate with UCLA Dental Clinic staff to identify patients and meet with them during their visit.

Patient recruiters such as dental surgeons will also be briefed on the nature of the study and the inclusion and exclusion criteria to assist in identifying potential patients for screening. During the

screening visit, the research team will confirm eligibility via the inclusion and exclusion criteria and explain the risks of the study to the patients.

Enrollment (Day 0)

1. Patients that are cleared through the screening eligibility and who voluntarily sign the informed consent will be enrolled into the study. The patient will be cleared through the screening eligibility based on the inclusion and exclusion criteria. If not suitable for the enrollment, the reason will be recorded on the Case Report Form.
2. An imaging stent will be created for the scanning. This stent, fabricated by the treatment team, bears radiopaque markers to provide location information on the CT scan, and typically requires lag time for laboratory fabrication. Patients will be scheduled for the CT scan by the research team, in coordination with the surgical team.

Study Procedure: DE-CBCT scan (Visit 1)

1. Patients scheduled for their imaging procedures will be confirmed by the research team via the name and date of birth and assigned an alphanumeric code.
2. For women in childbearing age, pregnancy status will be confirmed and recorded.
3. The region of interest (example: tooth number, potential implant site) that requires radiographic imaging will be recorded.
4. DE-CBCT: Prior to imaging, the DE-CBCT unit will be calibrated using a hydroxyapatite (HA) standard phantom. Calibration is performed by taking the images for three times with the tube energy settings of 60 kV / 90 kV. The device will be calibrated three times throughout the study period- prior to the initiation of the study, half the number of patients are recruited, before the end of the study.
 - The details of the HA phantom are as follows:
 - Manufacturer: QRM GmbH, Germany
 - Material: CaHP (Calcium Hydroxy Apatite)
 - HA Concentration (mg/cm³): 0, 100, 200, 400, 600, 800, 1000, 1200
 - Calibration protocol: ISO 9001 QM-System
5. Following the calibration, the research staff will acquire a DE-CBCT imaging. Either mandible or maxilla, depending on the tooth number (imaging site), will be imaged. The appropriate imaging mode will be selected depending on patient size and field of view, and the tube energy set at 60 kV / 90 kV. The DE-CBCT will be acquired with the imaging stent in place.
6. Subject will be scheduled for MDCT scan (Visit 2). The next visit must be within 30days after the visit
 1. Depending on the availability of scheduling on MDCT unit, Visit 2 may occur on the same day as Visit 1.
7. Before the patient returns home, the study staff will educate the subject to contact him/her if adverse events such as nausea, vomiting, hair loss, and oral inflammation occur.

Study Procedure: MDCT scan (Visit 2)

1. Patients scheduled for their MDCT imaging procedures will be confirmed by the imaging facility via the name and date of birth and assigned screening number.
2. For women in childbearing age, pregnancy status will be re-confirmed and recorded.
3. The region of interest (example: tooth number, potential implant site) that requires radiographic imaging will be recorded. The imaging site for MDCT scan will be identical to the one for DE-CBCT scan.
4. The patient will be imaged using the standard clinical protocol for MDCT, and simultaneous scanning of the calibration phantom (QRM-BDC/6).

8.2 Efficacy assessments

BD Assessment

In each patient's MDCT and DE-CBCT scans, discrete regions of interest (ROIs) will be made in the area where radiographic imaging is necessary for the dental diagnosis and treatment plan. The ROI will be angulated, sized, and positioned to mark the treatment area. Using the software tools, the BD will be assessed and recorded. The assessments at each location will be recorded and the HU values of DE-CBCT will be correlated with those of MDCT.

Assessments will be made independently by two oral and maxillofacial radiologists. Each radiologist will make these assessments twice, with at least one month between the two assessments.

8.3 Safety assessments

As described, the primary risk from the DE-CBCT examination is from ionizing radiation. With the low dose used in this procedure, we do not anticipate any deterministic radiation-related effects. The lack of such events will be documented after each examination.

8.4 Adverse events and serious adverse events

8.4.1 Definition of adverse event

An Adverse Event (AE) in this clinical trial includes any unfavorable and unintended signs, or symptoms associated with the use of DE-CBCT and CBCT, whether or not considered intervention related. AE may be expected (ex: symptoms related to deterministic radiation effects) or unexpected. Unexpected AE is a sign or symptom not identified in nature, severity, or frequency in the current Investigator's Brochure or of greater severity than expected based on the information in the Investigator's Brochure.

8.4.2 Serious adverse event

An adverse event (AE) or suspected adverse reaction is considered "serious" if, in the view of either the investigator or sponsor, it results in any of the following outcomes: death, a life-threatening adverse event, inpatient hospitalization or prolongation of existing hospitalization, a persistent or significant incapacity or substantial disruption of the ability to conduct normal life functions, or a congenital anomaly/birth defect. Important medical events that may not result in death, be life-threatening, or require hospitalization may be considered serious when, based upon appropriate medical judgment, they may jeopardize the participant and may require medical or surgical intervention to prevent one of the outcomes listed in this definition.

8.4.3 Classification of an adverse event

Severity of event

- **Mild** – Events require minimal or no treatment and do not interfere with the participant's daily activities.
- **Moderate** – Events result in a low level of inconvenience or concern with the therapeutic measures. Moderate events may cause some interference with functioning.
- **Severe** – Events interrupt a participant's usual daily activity and may require systemic drug therapy or other treatment. Severe events are usually potentially life-threatening or incapacitating. Of note, the term "severe" does not necessarily equate to "serious".

Relationship to study intervention

All adverse events (AEs) must have their relationship to study intervention assessed by the clinician who examines and evaluates the participant based on temporal relationship and his/her clinical judgment. The degree of certainty about causality will be graded using the categories below. In a clinical trial, the study product must always be suspect.

Related – The AE is known to occur with the study intervention, there is a reasonable possibility that the study intervention caused the AE, or there is a temporal relationship between the study intervention and event. Reasonable possibility means that there is evidence to suggest a causal relationship between the study intervention and the AE.

Not Related – There is not a reasonable possibility that the administration of the study intervention caused the event, there is no temporal relationship between the study intervention and event onset, or an alternate etiology has been established.

Expectedness

The Principal investigator in collaboration with the co-Investigators will be responsible for determining whether an adverse event (AE) is expected or unexpected. An AE will be considered unexpected if the nature, severity, or frequency of the event is not consistent with the risk information previously described for the study intervention.

The occurrence of an adverse event (AE) or serious adverse event (SAE) may come to the attention of study personnel during study visits and interviews of a study participant presenting for medical care, or upon review by a study monitor.

8.4.4 Time Period and Frequency for Event Assessment and Follow-Up

All AEs including local and systemic reactions not meeting the criteria for SAEs will be captured on the appropriate case report form (CRF). Information to be collected includes event description, time of onset, clinician's assessment of severity, relationship to study product (assessed only by those with the training and authority to make a diagnosis), and time of resolution/stabilization of the event. All AEs occurring while on study must be documented appropriately regardless of relationship. All AEs will be followed to adequate resolution.

Any medical condition that is present at the time that the participant is screened will be considered as baseline and not reported as an AE. However, if the study participant's condition deteriorates at any time during the study, it will be recorded as an AE.

Changes in the severity of an AE will be documented to allow an assessment of the duration of the event at each level of severity to be performed. AEs characterized as intermittent require documentation of onset and duration of each episode.

The PI or his designee will record all reportable events with start dates occurring any time after informed consent is obtained until 7 (for non-serious AEs) or 30 days (for SAEs) after the last day of study participation. At each study visit, the investigator will inquire about the occurrence of AE/SAEs since the last visit. Events will be followed for outcome information until resolution or stabilization.

8.4.5 Adverse event reporting

The PI/designee will record non-serious adverse events and report them to project sponsor within 30 working days after investigator first learns of the effect.

8.4.6 Serious adverse event reporting

The study investigator shall complete an Unanticipated Adverse Device Effect Form and submit to the study sponsor and to the reviewing Institutional Review Board (IRB) as soon as possible, but in no event later than 10 working days after the investigator first learns of the effect. The study sponsor is responsible for conducting an evaluation of an unanticipated adverse device effect and shall report the results of such evaluation to the Food and Drug Administration (FDA) and to all reviewing IRBs and participating investigators within 10 working days after the sponsor first receives notice of the effect. Thereafter, the sponsor shall submit such additional reports concerning the effect as FDA requests.

8.4.7 Reporting events to participants

Not applicable. The investigational device exposes subjects to low levels radiation and we do not anticipate any adverse events that require us to contact participants to ensure their health and safety.

8.4.8 Events of special interest

Not applicable.

8.4.9 Reporting of pregnancy

Not applicable.

9 STATISTICAL CONSIDERATIONS

In this study, we seek to recruit 24 patients to evaluate the effectiveness and safety of DE-CBCT for assessing jaw bone density compared to the current clinical gold standard for BD measurement, MDCT. This primary objective will be analyzed by correlating DE-CBCT HU values to MDCT HU values and Pearson will be performed for the correlation. The higher the correlation coefficient, the more DE-CBCT correlated to MDCT, meaning DE-CBCT is equivalent to the clinical use of MDCT.

To evaluate the accuracy of DE-CBCT and its equivalence to MDCT, we will analyze the agreement between the two methods using Bland-Altman plots.

To evaluate the intra- and inter-observer reliability, observer we will use Kappa statistics to:

1. Quantify the level of agreement between duplicate assessments by the same radiologist
2. Quantify the level of agreement between independent assessments by the two radiologists

Evaluation analysis group

In this clinical trial, the data from PP analysis group (Per-Protocol Analysis Set) will be analyzed.

① Per Protocol Analysis Set:

The PP analysis group includes subjects who complete the study according to the study plan without a significant violation of the protocol- from voluntarily agreeing to participate in the study to finishing the scanning of both DE-CBCT and MDCT. If the quality of image is affected by the metal prosthesis, the subject corresponding to the image is excluded from the PP analysis group.

② A major violation of the study plan to be excluded from the PP analysis group:

The quality of the image, especially the area where ROI is located, is degraded by the metal prosthesis.

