CBCT and HU: Assessment of BD has relevance in dentistry. The degree of mineralization of bone at dental implant sites are strong determinants of implant osseointegration and stability. Likewise, closer representation of attenuation and CT numbers are important for third party applications of CT data that use automatic segmentation for computer-aided design and computer-aided manufacturing applications. Current dental CBCT units do not apply a standard scaling system for representing CT numbers, and attempts to convert CBCT numbers to HU are unsuccessful. In particular, the cone beam geometry of the x-ray beam produces scatter radiation and consequently decrease the signal-to-noise ratio, with a practical negative impact on contrast resolution of the CBCT image.¹

Studies from our group and others have shown that although the relationship between CBCT numbers and object density is linear, this relationship is influenced by several factors including imaging protocol and anatomic location.⁹⁻¹⁵ Collectively, these factors result in an inhomogeneity of CT numbers on CBCT scans. For example, the CT number of the same object differed depending on the anatomical location in which it was imaged.¹⁵ Specifically, the CT numbers of phantom objects were higher when placed within the anterior region of the jaw and lower in the posterior regions.^{9,15} Importantly, objects with low x-ray attenuation suffered greater variability than objects with high attenuation.^{9,15} Moreover, these CT numbers are markedly influenced by scanner settings.¹¹ Due to these inconsistencies in CT numbers through the CBCT volume, it is not feasible to apply mathematical equations that will accurately derive HU through the CBCT volume. Nevertheless, there is promise to harness the power of CT imaging to decipher more than just morphological information. In a prior clinical study, CBCT gray values assessed at edentulous implant sites showed a trend of decreasing gray values with bone quality type.¹⁴

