Another widely used assessment, the Misch classification scheme, attempts to categorize subjective radiologic appearance based on a range of HU.¹⁷ Similar to the Lekholm and Zarb classification, this scheme is a subjective assessment, and this limits the depth of practical application for reliable prediction of successful osseointegration.

Misch classification of bone density.

TABLE 15.2 Misch Classification of Bone Density

Classification Type	Radiographic Appearance	Typical Anatomic Location	MDCT Density Range (HU)
D1	Primarily composed of dense cortical bone Marrow spaces are hardly visible	Occasionally in anterior mandible Rarely in posterior mandible	>1250
D2	Thick outer layer of porous cortical bone Coarse trabecular bone pattern	Commonly in anterior and posterior mandible Occasionally in anterior maxilla	850–1250
D3	Thinner layer of porous cortical bone Fine trabecular bone pattern	Commonly in anterior maxilla, posterior maxilla, and posterior mandible Occasionally in anterior mandible	350–850
D4	Faint to imperceptible outline of thin cortical bone Alveolar process is primarily composed of fine trabecular bone	Commonly in posterior maxilla Rarely in anterior maxilla	150–350

HU, Hounsfield units; MDCT, multidetector computed tomography.

Modified from Misch CE. *Contemporary Implant Dentistry*. 3rd ed. St. Louis: Mosby; 2008.

Pre-surgical assessment of bone quality is of high practical relevance. Success rates of implants placed in implants placed in D4 have lower success rates. Modifications to surgical techniques have been devised to improve osseointegration of implants placed in low density bone.¹⁸ In this study, jaw bone density assessed by DE-CBCT will be compared with that measured on MDCT, which is the gold standard for measuring bone density. The ability of DE-CBCT to provide information on jaw bone density could have tremendous impact on case selection and positively impact outcomes.

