5 STUDY POPULATION

5.1 *Rationale for Number of Subjects*

Based on the reference paper called "Bone quality evaluation at dental implant site using multislice CT, micro-CT, and cone beam CT," the correlation coefficient of human mandibular bone density (HU) between CBCT and MDCT was observed to be 0.89. In assumption that there also exists a correlation between the HU values of DE-CBCT images and MDCT images, Pearson's correlation analysis was considered for calculating the appropriate number of patients for the current study.

With 0.05 Type 1 Error (significance level 5%) and 80% statistical power, the number of patients is calculated to be 7. Further considering the three age groups and 10% of dropout rate will result in a total of 24 patients to be enrolled in the study.

Below is the hypothesis and calculation formula:

- Hypothesis:

Null hypothesis : $H_0 : \rho = 0$, Alternative hypothesis : $H_1 : \rho = r_0 \neq 0$

- Formula:

$$n = \left(\frac{z_{\alpha/2} + z_{\beta}}{C(r_0)} \right)^2 + 3, \quad C(r_0) = \frac{1}{2} \ln \left(\frac{1+r_0}{1-r_0} \right)$$

In : Log to the base of e

r_0 : Correlation coefficient value to be tested

α : Type 1 error

β : Type II error

$z_{\alpha/2}$: Value corresponding to $100(\alpha/2)\%$ in the standard normal distribution curve

z_{β} : Value corresponding to $100(\beta)\%$ in the standard normal distribution curve

- Calculation:

$$\textcircled{1} \quad \alpha=0.05, 1-\beta=0.80$$

$$\textcircled{2} \quad r_0=0.89$$

$$\begin{aligned} n &= \left(\frac{z_{\alpha/2} + z_{\beta}}{C(r_0)} \right)^2 + 3, \quad C(r_0) = \frac{1}{2} \ln \left(\frac{1+r_0}{1-r_0} \right) \\ &= \left(\frac{1.960 + 0.842}{1.422} \right)^2 + 3 = 6.88 \end{aligned}$$

$$\textcircled{3} \quad \text{Three age groups: } 7 \times 3 = 21$$

$$\textcircled{4} \quad \text{Dropout rate: 10\%, n=24}$$

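### One unadjusted Pearson r, with rho = 0 as the only stated null, cannot separate tracking of bone density from tracking of jaw location

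*Combined protocol and SAP*

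**What the plan says.** Section 9 sets the primary analysis: "This primary objective will be analyzed by correlating DE-CBCT HU values to MDCT HU values and Pearson will be performed for the correlation". It goes on to treat a larger coefficient as showing equivalence to clinical MDCT, and sets no value that r must reach. Bland-Altman plots are also planned, without acceptance limits and without a breakdown by region.

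Section 5.1 gives the only hypotheses: "Null hypothesis : $H_0 : \rho = 0$, Alternative hypothesis : $H_1 : \rho = r_0 \neq 0". On sample size: "With 0.05 Type 1 Error (significance level 5%) and 80% statistical power, the number of patients is calculated to be 7". The planning value comes from mandibles only: "the correlation coefficient of human mandibular bone density (HU) between CBCT and MDCT was observed to be 0.89".

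The jaw imaged depends on the tooth number (section 8.1), and regions of interest (ROIs) go where treatment requires them (section 8.2). Each subject contributes at least three sites (section 4.1). Recruitment is balanced on age group and sex, not on jaw or position.

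Section 2.2 reports, from earlier CBCT work, that "the CT numbers of phantom objects were higher when placed within the anterior region of the jaw and lower in the posterior regions". In its bone-density table the location entry for the densest class, D1, is "Occasionally in anterior mandible Rarely in posterior mandible", and the least dense class, D4, is common in the posterior maxilla but rare in the anterior maxilla. Section 8.1 already collects location: "The region of interest (example: tooth number, potential implant site) that requires radiographic imaging will be recorded".

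**The concern.** The trial asks whether the DE-CBCT reading follows bone density. A null of rho = 0 on pooled sites asks only whether the two readings are associated for any reason, location included. Within each jaw, true density and the known CBCT location artefact run in the same direction, so a reading that responds to position alone correlates with MDCT.

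Section 2.2 names this artefact among the reasons why HU cannot be derived from conventional CBCT, and section 2.1 presents DE-CBCT as designed to overcome the limits of conventional imaging. A pooled r that partly rewards the artefact is weak evidence on that claim. The choice of null also matters: against rho = 0, a small r is enough for significance.

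**Working it through.** **The plan's own figure.** Section 5.1: ((1.960 + 0.842)/1.422)² + 3 = 6.88, so 7. Then 7 × 3 = 21, and 21 × 1.1 = 23.1, so 24. This reproduces.

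**Smallest r significant against rho = 0 (two-sided 5%).** r = t/√(n − 2 + t²) gives 0.433 at n = 21 and 0.404 at n = 24. For three sites per subject taken as independent, it gives 0.248 at 63 sites (3 × 21) and 0.232 at 72 (3 × 24).

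**Assumptions (not in the documents).** Mean HU, read off the density bands: anterior mandible 1050, posterior mandible 825, anterior maxilla 675, posterior maxilla 425. Within-region SD 150 to 250, equal mix of the four regions, one independent pair per patient.

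**Ceiling on r from location alone.**
- Between-region variance: (306.25² + 81.25² + 68.75² + 318.75²)/4 = 51,680.
- Anterior mean 862.5, posterior mean 625, difference 237.5. Covariance of an anterior indicator with true HU: 237.5 × 0.25 = 59.375.
- A noiseless device that reads only position has r = 59.375/(0.5 × √V), where V is the total variance of true HU.
- SD 150: V = 74,180, r = 0.44. SD 250: V = 114,180, r = 0.35.

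**With device noise.** Let the reading be an anterior offset δ plus noise of SD 100, with no density information. Then r = 59.375δ/√(V(δ²/4 + 100²)), and the chance of a significant positive r is about 1 − Φ(1.96 − atanh(r)√(n − 3)). Example (δ = 200, SD 150, n = 24): r = 11,875/√(74,180 × 20,000) = 0.308, and 1 − Φ(1.96 − 0.319 × 4.583) = 31%.

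| Offset (noise SDs) | r | n = 21 | n = 24 |
|---|---|---|---|
| 1 | 0.16–0.19 | 10–13% | 11–15% |
| 2 | 0.25–0.31 | 19–27% | 21–31% |
| 3 | 0.29–0.36 | 25–36% | 28–41% |

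Nominal is 2.5%. Simulation agrees to within about one percentage point. The region-adjusted test stays at 2% to 3%.

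**Dependence on site mix.** In a second model, HU is drawn from the table's classes, with common/occasional/rare weighted 6/2/0.5, 6/3/1 or 10/2/0.5, D1 capped at 1600 HU, and offsets of 1, 2 or 4 noise SDs.
- Mandible only, or both jaws: r about 0.11 to 0.32. Positive rejection is about 8% to 33% at n = 24, and 14% to 78% at 63 to 72 sites treated as independent.
- Anterior mandible with posterior maxilla: r about 0.33 to 0.72.
- Posterior sites only: r about 0.
- Anterior maxilla with posterior mandible: r about −0.13 to −0.31.

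**A device that does read density** (within-region SD 200, so V = 51,680 + 40,000 = 91,680).
- Noise SD 150: pooled r = √(91,680/(91,680 + 22,500)) = 0.90; within-region r = 200/√(200² + 150²) = 0.80.
- With an anterior offset δ, pooled r = (V + 59.375δ)/√(V(V + noise² + δ²/4 + 118.75δ)). At noise 150 this gives 0.89 for 200 HU and 0.85 for 400 HU, and it falls further to about 0.82 for 500 HU.
- Noise SD 400: the 200 HU offset raises pooled r from 0.60 to 0.64.
- Within-region r does not react to the offset: 0.80 at noise 150 and 0.45 at noise 400, whatever the offset.

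**The case against.** Five points deserve weight.

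1. A device with no density information is an extreme case. Section 2.2 says CBCT numbers relate linearly to object density, and section 8.1 calibrates the unit on eight hydroxyapatite concentrations from 0 to 1200 mg/cm³. This stands: the rejection rates above are a worst case, with an assumed artefact size.
2. The artefact is reported for earlier CBCT. The documents neither give its size nor say that DE-CBCT retains it. This also stands, but pooled r could not settle the question either way.
3. Location alone gives a modest r, and section 9 reads r on a graded scale, so such a device would look poor beside 0.89. This largely stands. The exposure comes from pairing rho = 0 with no required value of r.
4. Differences between regions are real differences in density, so removing them narrows the question and lowers r for a sound device. This stands, and is why pooled r should be kept.
5. An adjusted correlation removes regional offsets, so it cannot show whether the artefact has been overcome. This stands: regional bias has to come from the Bland-Altman analysis, which is planned but not split by region.

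A reader might infer that the artefact always inflates r, or that location could carry the trial to an r near 0.89. The documents support neither. The anterior excess in density holds within a jaw, the direction can reverse across jaws, the site mix is not fixed, and in an equal mix a larger artefact lowers r for an accurate device.

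**Conclusion.** The point holds as a limit on interpretation. Neither a pooled r nor a rejection of rho = 0 separates density tracking from location, and section 9 treats r as evidence of equivalence. Under the stated region means and an equal mix, location alone reaches at most about 0.35 to 0.44, yet it rejects rho = 0 several times more often than the nominal 2.5%. Both size and sign depend on a site mix that the protocol leaves to clinical need.

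It would go too far to say that DE-CBCT has this artefact, that the trial would pass a useless device with a high r, or that the adjusted correlation should replace the pooled one. This is a cheap improvement to what the trial can conclude.

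**What to change.** In section 9 and the Synopsis:

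- Record the tooth number for every ROI and classify each ROI by jaw (maxilla/mandible) and position (anterior/posterior).
- Beside pooled r, report a correlation of DE-CBCT with MDCT HU adjusted for these four regions. Use standard errors or a bootstrap clustered by patient, since each subject gives at least three sites.
- Report the Bland-Altman mean difference for each region. This is the part that would show a remaining location artefact.
- State that pooled r, or rejection of rho = 0, does not by itself show that DE-CBCT tracks density or is equivalent to MDCT.

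Cost: no extra scans or patients, up to 3 degrees of freedom, and a lower adjusted r (for example 0.80 beside 0.90). Regional estimates will be imprecise: 63 to 72 sites is about 16 to 18 per region if evenly spread, and clinical need may not spread them evenly.

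Run the analysis over all patients. With 21 independent pairs, the adjusted test has 80% power for a within-region correlation of tanh(2.802/√15) = 0.62. Within an age group of 7, the same calculation needs tanh(2.802/√1) = 0.99, which is not useful.
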